## 9 ELIGIBILITY

---

Please note eligibility waivers to inclusion/exclusion criteria are not permitted. Participants must meet all of the inclusion criteria and none of the exclusion criteria.

### 9.1 Registration Eligibility Criteria

#### 9.1.1 Trial Registration Inclusion Criteria

1. At least 18 years old
2. A diagnosis of chronic lymphocytic leukaemia (CLL) or small lymphocytic lymphoma (SLL) (by 2018 iwCLL criteria)
3. World Health Organisation (WHO) performance status (PS) of 0, 1 or 2
4. Biochemical values must be within the following limits within 4 weeks prior to randomisation/or registration for the Clinical Need Cohort and at baseline:
  - Alanine aminotransferase (ALT)  $\leq 3$  x upper limit of normal (ULN) OR Aspartate aminotransferase (AST)  $\leq 3$  x ULN.
  - Total bilirubin  $\leq 1.5$  x ULN, unless bilirubin rise is due to Gilbert's syndrome or of non hepatic origin
5. Agree to follow the pregnancy prevention guidelines:

Women:

- Women of childbearing potential must agree to use a highly effective form of contraception, this must include a barrier method for participants using hormonal contraceptives, whilst receiving ibrutinib until 3 months after the last dose of ibrutinib\*.
- Agree not donate eggs (ova, oocytes) for the purposes of assisted reproduction

Men:

- Males must agree to practice effective barrier contraception whilst receiving ibrutinib until 3 months after the last dose of ibrutinib
- Agree to not donate sperm during whilst receiving ibrutinib until 3 months after the last dose of ibrutinib

All participants who are randomised to the pausing ibrutinib arm will not be required to follow this during treatment breaks, but must restart this once treatment with ibrutinib resumes.

6. Able to provide informed consent

\*Participants randomised to the pause/resume arm must adhere to this whilst receiving ibrutinib, but will not be required to follow contraceptive measures during the planned treatment breaks (see section 14.5)

#### 9.1.2 Trial Registration Exclusion Criteria

1. Pregnant females
2. Known intolerance or hereditary problems of galactose intolerance, total lactase deficiency or glucose-galactose malabsorption.
3. Receipt of live vaccination within 4 weeks prior to registration and for the duration of the study.

4. History or current evidence of Richter's transformation
5. Major surgery within 4 weeks prior to randomisation/or registration for the Clinical Need Cohort
6. Active infection
7. Concomitant warfarin (or equivalent vitamin K inhibitor)
8. Central nervous system involvement with CLL
9. Cardiac failure; including symptomatic cardiac failure not controlled by therapy, or unstable angina not adequately controlled by current therapy (in patients with a significant cardiac history the left ventricular function should be assessed and patients with severe impairment should be excluded)
10. Respiratory impairment (e.g. bronchiectasis or severe COPD)
11. Other severe, concurrent diseases or mental disorders that could interfere with their ability to participate in the study
12. Positive serology for Hepatitis B (HB) defined as a positive test for HBsAg. In addition, if negative for HBsAg but HBcAb positive (regardless of HBsAb status), a HB DNA test will be performed and if positive the patients will be excluded. During treatment, these participants should be monitored and managed to prevent HBV reactivation.
13. Positive serology for Hepatitis C (HC) defined as a positive test for HCAb, in which case reflexively perform a test for hepatitis C RNA (for example HCV RNA PCR). If positive the patients will be excluded.
14. Persisting severe pancytopenia (neutrophils  $<0.5 \times 10^9/L$  or platelets  $<50 \times 10^9/L$ ) unless due to direct marrow infiltration by CLL
15. Current treatment with prednisolone of  $>20\text{mg/day}$
16. Uncontrolled Active haemolysis
17. History of stroke or intracranial haemorrhage within 6 months prior to enrolment.
18. Requirement for treatment with a strong CYP3A inhibitor or inducer (see Appendix 7)
19. New treatment with two or more antiplatelet drugs, treatment that has been administered at a stable dose for at least 3 months prior to registration is permissible
20. Current treatment with any concomitant ACE inhibitors

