### 8.1 Overall design and plan of the study

The 'Randomisation Pathway' is designed as a prospective, multicentre, open-label, randomised, controlled, 2-arm, parallel-group, non-inferiority study to compare an intermittent treatment strategy (experimental arm) with continuous treatment (control arm) with ibrutinib for patients with CLL who have responded well to treatment with ibrutinib. The primary outcome for this pathway will be time to treatment strategy failure, defined as the first documented instance of active disease as defined by the 2018 iwCLL criteria (Appendix 1) that does not respond to treatment, or death from any cause.

At randomisation previously treated participants will have been receiving ibrutinib as their second- or subsequent-line of therapy for at least the previous 36 months, whilst front-line participants entering from the FLAIR trial will have received 6 years of treatment with ibrutinib. There is no restriction on maximum duration of treatment for the previously treated cohort prior to enrolment. The recruitment period is 6 years, and each participant will be followed up for at least 3 years after randomisation. Participants will receive treatment during the trials 6 year recruitment period and for the 3 years of follow up, meaning that participants will be on the trial for between 3-9 years, depending upon when they enter the trial. 800 patients will be entered into the Randomisation Pathway with the goal of observing 379 treatment failure or death events.

Participants will be randomised to either an intermittent treatment strategy or to continuous therapy. Treatment allocation (1:1) will be by minimisation with a random element incorporating the following three factors: centre, whether or not the participant was previously treated in FLAIR and minimal residual disease (MRD) level at randomisation.

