Participants randomised to the intermittent treatment arm will pause ibrutinib treatment immediately following randomisation, and restart when the restart criteria are met (see Section 13.8.3; the restart criteria do not indicate active disease as per 2018 iwCLL criteria). When the re-start criteria are met participants will receive ibrutinib (oral) 420mg per day (or other reduced dose, if that dose has been stable for the past 6 months and there are no unresolved toxicities) until treatment failure (active disease per 2018 iwCLL criteria) whilst on treatment or death. If these participants demonstrate active disease whilst on the planned treatment pause they will initially resume ibrutinib and the criteria for treatment failure would be met if they present with active disease at the next follow up (in which case the time to treatment failure would be backdated to when active disease was first demonstrated). Those randomised to the continuous treatment arm will receive ibrutinib (oral) 420mg per day (or other reduced dose, if that dose has been stable for the past 6 months and there are no unresolved toxicities) until treatment failure (active disease) as per 2018 iwCLL criteria or death.

The Clinical Need pathway is a prospective, national, multicentre, open-label, single-arm, non-randomised cohort to assess the safety and overall survival of patients receiving continuous ibrutinib treatment. Participants exiting the FLAIR trial who are not eligible for randomised study because they have signs of progressive or returning CLL after completing 6 years of ibrutinib treatment within FLAIR, but prior to entry into STATIC, can join the Clinical Need Cohort. Participants in the Clinical Need Cohort

will receive treatment during the trials 6 year recruitment period and for the 3 years of follow up, meaning that participants will be on the trial for between 3-9 years, depending upon when they enter the trial. Up to 30 patients are expected to enter into the Clinical Need Cohort. Patients will continue receiving continuous ibrutinib, either at the standard dose, or a stable reduced dose.

Front-line participants entering either the Randomisation pathway or the Clinical Need cohort from the FLAIR trial should enter STATIC on completion of treatment in FLAIR, with no break in therapy, with the exception of participants who have completed the 6 years of treatment in FLAIR prior to STATIC opening.

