#### **9.4.1 Previously Treated Participants Randomisation Inclusion criteria**

1. Meet all of the registration inclusion criteria
2. Currently receiving ibrutinib for at least the previous 36 months. There is no restriction on maximum duration of treatment prior to enrolment.
3. In clinical remission fulfilling all of the following:
  - a. no palpable lymph nodes;
  - b. no palpable spleen; and
4. Lymphocyte count below  $5 \times 10^9/L$  continuously for at least the 12 months before randomisation

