#### **9.4.2 Previously Treated Participants Randomisation Exclusion criteria**

1. Meet none of the registration exclusion criteria
2. Disease progression (according to 2018 iwCLL criteria)
3. Ibrutinib treatment break for toxicity/patient choice for more than 28 days in last 12 months
4. Any illness, disease or condition, such as active cancer or secondary primary malignancy (SPM), with a prognosis of less than 5 years

5. Patients with a creatinine clearance of less than 30ml/min (either measured or derived by the Cockcroft Gault formula or alternative locally approved formula).

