### 13.1 Local policies for COVID-19 (and / or similar)

In light of the COVID-19 pandemic (and / or similar pandemics or epidemics), sites may have implemented policies concerning the treatment and assessment of patients with CLL, for example in order to minimise hospital/clinic visits. Full blood counts are an essential component of the treatment in STATIC. If it is necessary for some of the 3-monthly follow-up appointments to be conducted remotely blood tests should be performed nearer the patient's home, for example by the GP, in order to minimise hospital/clinic visits. If implementation of these policies whilst treating STATIC participants results in a deviation from the protocol, sites should refer to Section 13.15 and follow the usual process for the reporting of protocol violations, if required.

Face-to-face clinic visits with a relevant medical professional will remain mandatory if there is evidence of a patient progressing, for example if they report noticing lymphadenopathy, in order to ensure the safety and wellbeing of participants. Furthermore, participants on the intermittent treatment pathway who are due to pause ibrutinib should continue to undergo face-to-face review to ensure there is no clinical evidence of disease before pausing treatment.

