5.3.5. Transformation to a more aggressive histology (Richter syndrome or Richter transformation). The diagnosis of Richter transformation should be established by lymph node or other tissue biopsy.

5.3.6. Occurrence of cytopenia (neutropenia, anaemia, or thrombocytopenia) directly attributable to CLL and unrelated to autoimmune cytopenias.

5.3.6.1. During therapy. Cytopenias may occur as a side effect of many therapies and should be assessed according to Table 5. During therapy, cytopenias cannot be used to define disease progression. Each protocol should define the amount of drug(s) to be administered with such cytopenias.

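### The exemption for CLL-caused severe cytopenia in exclusion 14 carries into randomisation, so a previously treated patient with it can meet every written criterion and be allocated to stop ibrutinib at once

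*Protocol*

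**What the plan says.** Exclusion 14 in Protocol 9.1.2 removes patients with persisting severe pancytopenia, specified as low neutrophils (<0.5 x10^9/L) or low platelets (<50 x10^9/L), "unless due to direct marrow infiltration by CLL". All participants are registered (10.4.3), and item 1 of 9.4.2 requires previously treated patients to meet none of the registration exclusions before randomisation. The exemption comes with the list.

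Section 9.4.1 asks that these patients be on ibrutinib, with 36 months or more of it behind them, and be "In clinical remission fulfilling all of the following": no palpable nodes and no palpable spleen, with a lymphocyte count under 5 x10^9/L over the preceding 12 months. Section 13.8.3 uses the same three measures as the initial pause criteria. Item 2 of 9.4.2 excludes disease progression by the 2018 iwCLL criteria.

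Section 8.1 describes the Randomisation Pathway as being "for patients with CLL who have responded well to treatment with ibrutinib". It also says that participants in the intermittent arm "will pause ibrutinib treatment immediately following randomisation".

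**The concern.** The exemption makes sense where ibrutinib continues, as in the Clinical Need Cohort: a patient whose marrow is infiltrated should not lose access to treatment because of it. In the Randomisation Pathway half of the patients are told to stop, yet the exemption is unchanged. It lets in a patient precisely because CLL is judged to be the cause of a severe cytopenia, while the remission definition looks at neither platelets, neutrophils nor marrow.

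Two things are at stake. The first is the safety of a patient who has CLL-attributed marrow failure and is randomised to an immediate pause. The second is the match between the patients enrolled and the question asked, which is whether patients who have done well on ibrutinib can pause.

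The point concerns previously treated patients. They are on ibrutinib through routine commissioning (11.1.1) and would otherwise continue it, so allocation in STATIC is what causes the stop.

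**Working it through.** The protocol states no figure on this point to reproduce. The check traces the criteria for one hypothetical patient: previously treated, on ibrutinib for over 36 months, no palpable nodes or spleen, lymphocytes <5 x10^9/L for 12 months, and stable platelets <50 x10^9/L attributed to CLL in the marrow.

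**Eligibility**

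| Step | Place in Protocol | Result |
|---|---|---|
| Severe cytopenia exclusion | 9.1.2, item 14 | Not excluded: exempt because the cause is CLL |
| Registration exclusions applied to randomisation | 9.4.2, item 1 | Not excluded: exemption carried over |
| Clinical remission | 9.4.1, items 3 and 4 | Met: no platelet, neutrophil or marrow component |
| iwCLL progression | 9.4.2, item 2 | Not reliably excluded (see below) |
| Treatment break, short prognosis, creatinine clearance | 9.4.2, items 3 to 5 | Unrelated to the cytopenia |
| Active disease | 9.2.2, item 2 | Listed only for the Clinical Need Cohort |
| Initial pause criteria | 13.8.3 | Met: same three measures as remission |

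**The progression exclusion.** Appendix 1, 5.3.6, does list as progression "Occurrence of cytopenia (neutropenia, anaemia, or thrombocytopenia) directly attributable to CLL and unrelated to autoimmune cytopenias". But 5.3.6.1 then says "During therapy, cytopenias cannot be used to define disease progression", and this patient is on therapy by definition. Table 4 requires a platelet fall of at least 50% or a haemoglobin fall of at least 2 g/dL from baseline, secondary to CLL, and has no neutrophil row. A low count that persists unchanged is not such a fall. A new CLL-attributed fall might be caught; a stable one is not reliably caught.

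**After the pause.** The only blood count among the restart criteria in 13.8.3 is the lymphocyte count. The marrow item in the active-disease definition (13.10.1) needs new or worsening anaemia or thrombocytopenia. A stable low platelet count does not meet it, and neutropenia is not named in it. The full blood count every 3 months (13.8.1) would show worsening anaemia or thrombocytopenia, and a patient with active disease during a pause resumes ibrutinib (8.1, 12.5).

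**Depth of the exempted level.** 13.10.1 gives platelets <100 x10^9/L as a level generally taken to call for treatment, while noting that some patients stay stable below it. The exempted level is 50/100 = half of that.

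**Size.** The protocol gives no prevalence. The 0.1% to 1% below is an assumption, used only to show scale.

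- Previously treated patients: 0.55 x 800 = 440 (share and total from section 3).
- Randomised with this cytopenia: 440 x 0.001 = 0.44 to 440 x 0.01 = 4.4.
- Paused under 1:1 allocation: 0.44/2 = 0.22 to 4.4/2 = 2.2.

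**The case against.** The strongest reply is that several safeguards already stand between this patient and a pause. A medically qualified doctor must decide and document eligibility (10.2, 10.4.4). Appendix 1 is ambiguous rather than silent: 5.3.6 names CLL-attributed cytopenia as progression, and 5.3.6.1 opens by discussing cytopenia as a side effect of treatment, so an investigator could reasonably exclude the patient under 9.4.2, item 2. Clinicians may alter treatment at any time (12.4), and 3-monthly counts would reveal deterioration. The patient is also an unlikely one: severe marrow failure from CLL with no palpable nodes or spleen and a controlled lymphocyte count for a year.

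Much of this stands and keeps the point minor. It does not close the gap, because the doctor certifies against written criteria that expressly exempt this patient, and the ambiguity in Appendix 1 can be read either way.

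A reader might infer more than the documents support:

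- *That 13.1 is contradicted.* That section asks for face-to-face review "to ensure there is no clinical evidence of disease before pausing treatment". It is a rule about visit mode under pandemic policies. If it bears on the point, it is a partial safeguard.
- *That the blood-count schedule is inconsistent.* Section 13.7.1 marks the baseline full blood count as not mandatory for eligibility, and the pre-registration count in Appendix 4 carries no such mark. But the Appendix 4 column that matches 13.7.1 is the post-registration baseline, and there the count is marked not mandatory. The two agree.
- *That FLAIR patients need the same change.* Ibrutinib in FLAIR was scheduled to stop at 6 years (6.3), so STATIC does not cause their stop.
- *That pausing would demonstrably worsen the cytopenia.* A patient still this cytopenic after 36 months of ibrutinib may or may not be having that cytopenia held in check by the drug. The documents do not say.

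**Conclusion.** The gap is real and narrow. On the written criteria, a previously treated patient with stable, CLL-caused neutrophils <0.5 or platelets <50 x10^9/L can be randomised and told to stop ibrutinib at once, which does not fit the population described in 8.1. The conclusion rests on the cytopenia being stable and on 5.3.6.1 being read as it is worded; 5.3.6 leaves some room for a stricter reading.

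It is a minor patient-safety and target-population correction. On the assumed 0.1% to 1%, between 0.2 and 2.2 such patients would be paused in the whole trial. A reader might suspect bias in the primary comparison. Nothing in the documents supports that at these numbers, and no effect on the hazard ratio is claimed.

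**What to change.** Add one exclusion to 9.4.2: persisting neutrophils <0.5 x10^9/L or platelets <50 x10^9/L from any cause, including marrow infiltration by CLL. Check it on the full blood count that Appendix 4 already schedules before registration. The clinical team should confirm the thresholds. Leave 9.1.2, 9.2.1, 9.3.2 and 13.7.1 as they are.

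The cost is one line of text and no new test. On the assumed range, 0.4 to 4.4 previously treated patients become ineligible; the upper figure is 4.4/800 = 0.55% of the target, or 4.4/12 = about 0.4 of a month of recruitment at the planned 12 per month. Those patients keep ibrutinib through routine commissioning.

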## 9.2 Clinical Need Cohort Registration for Front-line Patients

Participants in the Clinical Need Cohort will need to meet the following additional eligibility criteria:

### 9.2.1 Clinical Need Cohort Inclusion Criteria

1. Meet all of the Registration Inclusion criteria
2. Currently receiving ibrutinib and nearing the end or having completed 6 years of ibrutinib treatment on FLAIR\*
3. Have signs of progressive or returning CLL after completing 6 years of ibrutinib treatment within FLAIR, but prior to entry into STATIC

\* Patients should enter STATIC on completion of treatment in FLAIR, with no break in therapy, with the exception of participants who have completed the 6 years of treatment in FLAIR prior to STATIC opening

### 9.2.2 Clinical Need Cohort Exclusion criteria

1. Meet none of the registration exclusion criteria
2. Active Disease, as per the 2018 iwCLL criteria requiring an alternative therapy.

3. Received treatment other than ibrutinib for CLL since completing FLAIR
4. Be eligible for front-line randomisation (see section 9.3)

### **9.3 Front-Line: Randomisation Eligibility Criteria**

Front-line participants who enter the Randomisation Pathway will need to meet the following additional eligibility criteria:

#### **9.3.1 Front-Line Randomisation Inclusion criteria**

1. Meet all of the Registration Inclusion criteria
2. Currently receiving ibrutinib in FLAIR or having completed 6 years of ibrutinib of ibrutinib in FLAIR\*
3. In clinical remission all of the following:
  - a. no palpable lymph nodes;
  - b. no palpable spleen; and
4. lymphocyte count below  $5 \times 10^9/L$  continuously for at least the 12 months before randomisation

\* Patients should enter STATIC on completion of treatment in FLAIR, with no break in therapy, with the exception of participants who have completed the 6 years of treatment in FLAIR prior to STATIC opening

#### **9.3.2 Front-Line Randomisation Exclusion criteria**

1. Meet none of the registration exclusion criteria
2. Disease progression (according to 2018 iwCLL criteria)
3. Ibrutinib treatment break for toxicity/patient choice for more than 28 days in last 12 months

### **9.4 Previously Treated Participants Randomisation Eligibility Criteria**

Previously treated participants who enter the Randomisation Pathway will need to meet the following additional eligibility criteria:

#### **9.4.1 Previously Treated Participants Randomisation Inclusion criteria**

1. Meet all of the registration inclusion criteria
2. Currently receiving ibrutinib for at least the previous 36 months. There is no restriction on maximum duration of treatment prior to enrolment.
3. In clinical remission fulfilling all of the following:
  - a. no palpable lymph nodes;
  - b. no palpable spleen; and
4. Lymphocyte count below  $5 \times 10^9/L$  continuously for at least the 12 months before randomisation

#### **9.4.2 Previously Treated Participants Randomisation Exclusion criteria**

1. Meet none of the registration exclusion criteria
2. Disease progression (according to 2018 iwCLL criteria)
3. Ibrutinib treatment break for toxicity/patient choice for more than 28 days in last 12 months
4. Any illness, disease or condition, such as active cancer or secondary primary malignancy (SPM), with a prognosis of less than 5 years

5. Patients with a creatinine clearance of less than 30ml/min (either measured or derived by the Cockcroft Gault formula or alternative locally approved formula).

# 10 RECRUITMENT PROCESS

---

## 10.1 Study setting

The trial will be conducted in 100 NHS Centres in the UK (England, Wales, Scotland and Northern Ireland) the majority of which are already participating in the FLAIR trial. All centres will be experienced in multidisciplinary diagnosis and management of CLL and have an established research infrastructure, including clinical research nurses funded via the NIHR CRN. Centres will be identified via a feasibility assessment to determine those most appropriate to participate in the trial. Research centres will be required to confirm capacity and capability and undertake site initiation training with the Clinical Trials Research Unit (CTRU) prior to the start of recruitment into the trial. Screening and recruitment processes must not be initiated at site until approval to open to recruitment has been formally issued by the CTRU.

800 participants will be recruited over 6 years into the randomisation pathways. Participants treated in an ibrutinib-based arm of the FLAIR trial should be approached by the research team during routine clinic appointments. Additionally, participants with previously treated CLL who have already been treated in second or subsequent line of therapy with ibrutinib for at least 3 years (not in the FLAIR trial) will be identified during routine clinic appointments.

Participants entering the Clinical Need Cohort will be recruited over 6 years. Participants who have been treated with an ibrutinib-based arm of the FLAIR trial may be eligible to enter the STATIC Clinical Need Cohort and will be identified during routine clinic appointments.

Patients from FLAIR entering either the randomisation trial or the Patient Need Cohort must enter STATIC with no break in therapy, with the exception of participants who have completed the 6 years of treatment in FLAIR prior to STATIC opening. Where possible these potential participants should be approached prior to the final routine 3 monthly appointment on FLAIR in order to prevent any break in therapy.

Information about the trial will also be shared with patient support groups as well as the distribution of leaflets via support groups and hospital clinics.

Invitation to participate in the trial and provision of information can be made either in person during routine hospital visits or via telephone/video consultations.

